5.1.2 Secondary Endpoints Definitions

Objective Response (OR) per RECIST 1.1:

Objective Response is defined as a best overall response ([Appendix C](#)) of either Complete Response (CR) or Partial Response (PR) per RECIST 1.1. Radiographic response (Complete Response, Partial Response) requires confirmation by a repeat, **evaluable** scan at least 28 days after the first documentation of response.

Subjects who do not experience a PR/CR or do not have any follow-up tumor assessments will be regarded as non-responders.

Overall Survival (OS):

Overall survival is defined as the time from the date of Study Day 1 until death due to any cause:

$$\text{OS time (Days)} = \text{date of death} - \text{Study Day 1} + 1.$$

Any subject not known to have died at the time of analysis will be censored based on the last recorded date on which the subject was alive.

Duration of Response (DOR):

The duration of response is defined as time from first evidence of CR or PR to disease progression or death due to any cause, whichever occurs first. DOR will be calculated only for subjects who achieve a best overall response of PR or CR.

$$\text{DOR (months)} = (\text{PD / death date} - \text{response start date} + 1) \times 12 / 365.25$$

The time of the initial response will be defined as the earliest of the dates contributing towards the first visit response of PR or CR.

- For confirmed responders whose PR or CR are confirmed in two **evaluable** assessments, the first PR/CR assessment among the two **evaluable** assessments will be used to calculate DOR.
- For unconfirmed responders awaiting follow-up confirmation scans, the PR or CR assessment that is awaiting confirmation scan will be used to calculate DOR.

Censoring rules for Duration of Response (DOR):

- Data for responders who are alive and without disease progression or new anti-cancer therapy are censored at the time of last **evaluable** tumor assessment **by CT/MRI scan**.
- Data for responders who are alive and without disease progression but who start new anti-cancer therapy are censored at the time of last **evaluable** tumor assessment **by CT/MRI scan** before the start of new anti-cancer therapy.
- Data for responders who die or have disease progression after two or more missed evaluable tumor assessments are censored at the time of last evaluable tumor assessments **by CT/MRI scan** before the two or more missed evaluable tumor assessments.

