True Grade 4 or Higher Treatment-related Adverse Event Rate	Probability of Early Stopping of Dose Expansion	Average Dose Expansion Sample Size
0.10	2.0%	39.5
0.15	9.1%	37.6

0.20	23.2%	33.9
0.25	42.2%	28.8
0.30	61.6%	23.4

A formal interim analysis of available safety and efficacy data will occur when the first 10 evaluable subjects enrolled have had the opportunity to complete 4 months on study. This interim analysis will estimate MTD, support the determination of RP2D, conduct futility analysis of objective response rate (ORR), and support the evaluation of benefit/risk profile of AMG 160 as a monotherapy.

When deemed necessary, the scope of this interim analysis may include other endpoints mentioned in [Section 2.1](#) if applicable. However, analysis of DOR and time-to-event endpoints will not be conducted unless there are more than 10 events.

[figure not shown]
A futility analysis of ORR will be performed using Bayesian predictive probability (Lee and Liu, 2008) when the first 10 evaluable subjects reach month 4. If the predictive probability of observing ORR response > 15% at the end of the study with 50 evaluable subjects is less than 30%, the study may stop early (pT = 0.25). Equivalently, if we observe ≥ 1 objective responder in the first 10 subjects, an additional subjects (up to 40) will be enrolled into the expansion cohort. The predictive probability is calculated with a noninformative prior, Jeffreys prior, Beta(0.5, 0.5).

Similarly, futility analysis will also be conducted during the expansion cohort. The stopping boundaries are presented in [Table 7-3](#). The operating characteristics in [Figure 7-1](#) provide the probability of stopping the trial early for given hypothetical true rate of ORR.

Table 7-3. Objective Response Rate Stopping Boundary

Number of Evaluable Subjects Each Month 4	Stop Study if Observed Objective Response Rate (ORR) Response
10	< 1
20	< 2
30	< 3
40	< 4
50	Study Complete

Figure 7-1. The Probability of Stopping The Trial Early

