Appendix C. RECIST (v1.1) Criteria

The protocol requires that a PD must be confirmed. The analysis of modified RECIST 1.1 BOR endpoints will follow standard RECIST 1.1 convention which does not require confirmation of PD.

Objective response (OR) per Response Evaluation Criteria in Solid Tumors (RECIST) 1.1

Timepoint Response by Investigator:

Timepoint response by Investigator is the overall tumor response collected on the Overall Response modified RECIST 1.1 CRF at each tumor assessment.

Confirmed BOR by Investigator:

Best Overall Response (BOR) by Investigator is derived from the timepoint response by investigator using RECIST 1.1 criteria. At each time point, BOR will be derived based upon the evaluated time points up to and including the current assessment. The following rules will apply to BOR:

- CR is better than PR; PR is better than SD; SD is better than PD; PD is better than NE.
- For a BOR of SD, a duration of SD \geq 49 days since study day 1 is required.
- For a BOR of CR and PR, confirmation is required **by a repeat assessment at least** \geq 28 days after the initially observed assessment of CR or PR
 - A CR must be confirmed by CR, a PR can be confirmed by a PR or CR.
 - **For confirmation of PR or CR**, an unlimited number of intermittent assessments of NE can occur between the initial response and the confirmation. For example, BL, CR, NE, NE, NE, CR – the CR at post-baseline 1st **assessment** is confirmed at post-baseline 5th **assessment**.
 - **For confirmation of PR**, an unlimited number of intermittent assessments of SD can occur between the initial PR and the confirmation. It is reasonable to consider a patient with time point response of PR-SD-SD-PR as a confirmed response i.e., **confirmed PR**.

[Table 14.1](#) provides the BOR determination per RECIST 1.1 for trials where confirmation of response is required. A BOR determined by [Table 14.1](#) is considered as confirmed

BOR. [Table 14.2](#) outlines the steps to derive Confirmed_BOR (step 1) given investigator's timepoint assessments.

Interim BOR by Investigator:

At interim futility analysis, due to lack of sufficient follow-up time for confirmation scan, study team may choose to report both confirmed responders and unconfirmed responders (subjects had an initial PR or CR and still has potential for future confirmative scans). Interim BOR is defined to include unconfirmed responders in addition to those who achieve confirmed BOR.

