Timepoint Response by Central Review:

Timepoint response by Central Review is the Overall response at each tumor assessment as assessed by Central radiographic reader(s). This data is usually non-CTDB dataset transferred from Central Review vendor.

Confirmed BOR by Central Review:

Confirmed BOR by Central Review will be derived from the Timepoint Response by Central Review in the same way as Confirmed BOR by Investigator.

Interim BOR by Central Review:

Interim BOR by Central Review will be derived from Timepoint response by Central Review in the same way as Interim BOR by Investigator.

Best Overall Response (BOR):

The best overall response is the best observed disease response recorded from the start of the study treatment until disease progression/recurrence, the start of new anticancer therapy or the end of study. Confirmed BOR by Investigator, Interim BOR by Investigator, Confirmed BOR by Central Review, Interim BOR by Central Review have been separately defined above.

The followings steps would be followed to derive ORR as per RECIST 1.1.

Table 14.1. BOR per RECIST 1.1 where confirmation of CR/PR is required

[figure not shown]
Criterion	Time point T1 Response	T1 ≥ 49 days after Baseline?	Time point T2 Response	T2 ≥ 49 days after Baseline?	T2 ≥ 28 days after T1?	Confirmation	
C1	CR	Yes	CR	-	Yes	CR	
C2			CR	-	No	SD	
C3			PR, SD	-	-	Query data*	
C4			PD	-	-	SD	
C5			NE, No further evaluations			SD	
C6		No		CR	-	Yes	CR
C7				CR	Yes	No	SD
C8				PR, SD	-	-	Query data*
C9				PD	-	-	PD
C10				NE, No further evaluations			NE
C11	PR	Yes	CR, PR	-	Yes	PR	
C12			CR, PR	-	No	SD	
C13			SD	-	-	SD	
C14			PD	-	-	SD	
C15			NE, No further evaluations			SD	
C16		No		CR, PR	-	Yes	PR
C17				CR, PR	Yes	No	SD
C18				SD	Yes	-	SD
C19				PD	-	-	PD
C20				NE, No further evaluations			NE
C21	SD	Yes	CR, PR, SD, PD, NE, no more evaluation			SD	
C22			No	CR, PR, SD	Yes	-	SD
C23		CR, PR, SD		No	-	NE	
C24		PD		-	-	PD	
C25		NE, No further evaluations			NE		
C26	PD		-		PD		
C27	NE	-	NE, No further evaluations			NE	
C28		-	CR, PR, SD	Yes	-	SD	
C29		-	CR, PR, SD	No	-	NE	
C30		-	PD	-	-	PD	

CR = complete response, PR = partial response, SD = stable disease, PD = progressive disease, and NE = not evaluable.

*If a CR is truly met at first time point, then any disease seen at a subsequent time point, even disease meeting PR criteria relative to baseline, makes the disease PD at that point (since disease must have reappeared after CR). Best response would depend on

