whether minimum duration for SD was met. However, sometimes 'CR' may be claimed when subsequent scans suggest small lesions were likely still present and in fact the patient had PR, not CR at the first time point. Under these circumstances, the original CR should be changed to PR and the best response is PR.

Note: The UE response collected on eCRF will be mapped to NE for all the derivations and analysis.

Deriving Objective Response Rate (ORR) per RECIST 1.1

ORR is defined as the proportion of subjects with Objective Response while on study as defined by RECIST 1.1. All subjects that do not meet the criteria for objective response by the analysis cut-off date will be considered as non-responders.

$$\text{ORR} = (\text{Number of Subjects with Objective Response}) / \text{Total number of subjects in the analysis set.}$$

Note: Study allows NE between CR and its confirmation scan (CR-NE-CR), and NE/SD between PR and its confirmation scan (PR-SD-PR or PR-NE-PR).

Note: We will be deriving two sets of ORR and **presenting**, namely Objective Response Rate by Central Review and Objective Response Rate by Investigator Review.

Unconfirmed Responses for Interim Analysis

For a study where CR/PR confirmation is required, due to lack of sufficient follow-up time at interim analysis, both confirmed responders and unconfirmed responders will be reported. Subjects with any objective response (i.e., CR or PR) that is not confirmed as defined in [Section 5.1.2](#) will be summarized based on below definitions.

Interim response of unconfirmed CR awaiting confirmatory scan:

A subject will have an interim response of unconfirmed CR awaiting confirmatory scan if and only if each of the following requirements is met: 1) the confirmed best overall response is not a confirmed CR and 2) the last evaluable tumor assessment prior to data cutoff (DCO) is a CR and 3) none of the following events are recorded (end of study date, death date, new anti-cancer therapy, end of radiographic follow up date, progression date).

Interim response of unconfirmed PR awaiting confirmatory scan:

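### The footnote to SAP Table 14.1 gives a relabelled CR a best response of PR with no confirmation condition, against the table's own PR rows, so an unconfirmed PR could be counted in the final ORR and DOR.

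*SAP*

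**What the plan says.** SAP Appendix C derives best overall response (BOR) from pairs of time-point responses in Table 14.1, titled "BOR per RECIST 1.1 where confirmation of CR/PR is required". The text before the table states the general rule, "For a BOR of CR and PR, confirmation is required", by a repeat assessment at least 28 days later, and adds "A CR must be confirmed by CR, a PR can be confirmed by a PR or CR". Intervening NE assessments are allowed, and for PR also intervening SD. The same text says that a BOR determined by Table 14.1 counts as a confirmed BOR. SAP 5.1.2 defines objective response in matching terms: "Radiographic response (Complete Response, Partial Response) requires confirmation by a repeat", evaluable scan at least 28 days after the first.

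Rows C3 and C8 cover a CR at T1 followed by PR or SD at T2. Their result is a data query with an asterisk, and the T1-to-T2 interval column holds a dash. The footnote has two branches:

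- True CR: "If a CR is truly met at first time point, then any disease seen at a subsequent time point" is PD at that point, and best response depends on the minimum duration for SD.
- Misread CR: the footnote allows that "sometimes 'CR' may be claimed when subsequent scans suggest small lesions were likely still present and in fact the patient had PR, not CR at" T1. For that case it rules as follows: "Under these circumstances, the original CR should be changed to PR and the best response is PR".

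The second branch states no interval and no confirming scan, and does not send the reader back to the PR rows.

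**The concern.** The footnote fixes the final best response, not only the T1 label. Once T1 is PR, the table already has rows for what follows, and some of them give SD where the footnote gives PR. The SAP does not say which text prevails, so two programmers could derive different best responses for the same subject.

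The consequence could reach the reported results. A PR assigned through Table 14.1 can pass as confirmed, and it then fails the first condition of the Appendix C categories for unconfirmed PR, so it would not be shown there as unconfirmed. ORR counts subjects with an objective response, and SAP 5.1.2 computes DOR for any subject whose best overall response is PR or CR. The relabelling is made after T2 is known, in an open-label study, and compared with the PR rows it can only keep or raise the number of responders.

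**Working it through.** **1. Footnote against the PR rows.** Relabel T1 from CR to PR and re-enter Table 14.1:

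| Claimed sequence | After relabelling | PR rows give | Footnote gives |
|---|---|---|---|
| CR, then PR at 28 days or more | PR, PR | PR (C11, C16) | PR |
| CR, then PR in under 28 days | PR, PR | SD (C12, C17) | PR |
| CR, then SD at any interval | PR, SD | SD (C13, C18) | PR |

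C17 and C18 also need T2 to be at least 49 days after baseline. The first line agrees; the other two conflict. The conflict remains only if no later PR or CR confirms the response, because Appendix C accepts a sequence such as PR-SD-PR.

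**2. How often the conflicting lines can arise.**

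- *Early PR.* Protocol Table 1-6 sets CT/MRI every 8 weeks, each scan ± 7 days. The shortest gap between scheduled scans is 56 − 14 = 42 days. A T2 under 28 days after T1 needs an unscheduled scan.
- *CR then SD.* Under Protocol Appendix 12, SD at T2 means a target-lesion sum more than 70% of baseline, while PD is a rise from nadir of at least 20% and at least 5 mm. From a near-zero T1 sum, a return above 70% of baseline normally meets PD. If target lesions are gone and non-target lesions remain, the overall response is PR, not SD. A borderline node is an exception. As an illustration with assumed measurements: a single target node of 15 mm at baseline is read as 9 mm at T1 (under 10 mm, CR), is re-read as 10 mm (33% decrease, PR), and measures 11 mm at T2. Then 1 − 11/15 = 27% decrease, which is not PR, and the rise of 1 mm from nadir is not PD, so T2 is SD.

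**3. Effect on final ORR.** The plan's own figure (SAP 3.2) is 40 subjects, 20% response, exact 95% CI 9% to 36%. Clopper-Pearson for 8/40 gives 9.05% to 35.65%, so it reproduces. If one of the eight is a footnote PR:

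- 8/40 = 20.0%, 95% CI 9.1% to 35.6%
- 7/40 = 17.5%, 95% CI 7.3% to 32.8%
- difference 1/40 = 2.5 points

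**4. Effect on the futility looks.** Inputs from SAP 7.1: Beta(0.5, 0.5) prior, final n = 50, reference rate 15%, pT = 0.25, stop if predictive probability is below 30%. I take success at n = 50 as posterior P(ORR > 15%) > 0.25. With x responders the posterior is Beta(0.5 + x, 50.5 − x). This probability is 0.161 at x = 5 and 0.287 at x = 6, so success is at least 6/50. The predictive probability is the beta-binomial probability of reaching 6.

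| Look | Responders: probability | Responders: probability | SAP Table 7-3 stops if |
|---|---|---|---|
| 10 | 0: 9.5% | 1: 49.5% | < 1 |
| 20 | 1: 13.3% | 2: 43.8% | < 2 |
| 30 | 2: 11.6% | 3: 38.3% | < 3 |
| 40 | 3: 6.6% | 4: 30.1% | < 4 |

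Every boundary in Table 7-3 reproduces. At each look, one responder at the margin crosses the 30% cut-off. Reading success instead as an observed rate above 15% (at least 8/50) gives 21.3% at 2/20, 11.4% at 3/30 and 3.1% at 4/40, all below 30%, although Table 7-3 continues there. That reading is therefore not the plan's rule.

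**The case against.** The strongest reply is that the footnote only corrects a misread time point. Rows C3 and C8 raise a query, not a response. Confirmation is required in the Appendix C bullets, SAP 5.1.2, SAP Appendix D, Protocol 8.2.2 and Protocol Appendix 12, and Appendix C makes everyone who does not meet the objective-response criteria a non-responder. On that reading the corrected PR still has to be confirmed. This stands as far as it goes: a reader might infer that unconfirmed responders do enter ORR, and the documents do not settle that. But the footnote speaks of best response, and Appendix C treats a Table 14.1 result as confirmed, so the literal reading is equally available.

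A reader might also infer that one footnote PR opens Part 2, since SAP 7.1 continues "if we observe ≥ 1 objective responder in the first 10 subjects". For subjects still in follow-up the footnote is not what does this. Appendix C already lets unconfirmed responders be reported at interim, and a subject whose last evaluable non-SD assessment is PR, with no terminating event, counts as awaiting confirmation. A relabelled PR-SD subject, or one with PR again in under 28 days, meets that definition with or without the footnote. SAP 5.1.2 also admits such subjects to DOR. The footnote adds an interim responder only after progression, death, new therapy, or end of study or radiographic follow-up has ended that status.

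Finally, ORR is a secondary, descriptive endpoint with no hypothesis test, and it is presented by central review as well as by investigator. Both points limit the consequences. Neither removes the conflict, since the same derivation applies to both reviews.

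**Conclusion.** The footnote conflicts with rows C12, C13, C17 and C18 and with the 28-day confirmation rule. Read literally, it could place an unconfirmed PR in the final ORR and DOR. The ordinary case, a PR at 28 days or more, is unaffected.

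The documents give no frequency for misread CRs. My assumption is 0 to 1 affected subject, given the 42-day minimum between scheduled scans and the rarity of SD after a near-complete response. One subject is worth 2.5 points of ORR at n = 40. At the first futility look the difference between 0/10 and 1/10 is 9.5% against 49.5% predictive probability, but the footnote accounts for it only if that subject is no longer awaiting a confirmatory scan. These two figures rest on reading pT = 0.25 as the posterior threshold, which Table 7-3 supports. This is a small inconsistency worth correcting before database lock, not evidence that the reported ORR will be inflated.

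**What to change.** Replace the last sentence of the footnote to SAP Table 14.1 with:

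> The original CR is changed to PR and the best response is then re-derived from rows C11 to C20 and the Appendix C confirmation rules, so a PR still needs a PR or CR at least 28 days later (intervening SD or NE allowed).

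This keeps a legitimate PR-SD-PR confirmation and needs no new data. The cost is one sentence in the SAP and the matching line of the derivation program; ORR may come out slightly less favourable.

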Appendix D. Additional Definition

Information described below will be reported from eCRF

Partial Response (PR):

Partial response (PR) is defined as at least a 30% decrease in the sum of longest diameters of target lesions, taking as reference the baseline sum diameters. There can be no appearance of new lesions.

Complete disappearance of all index lesions with presence of non-index lesions.

Confirmation scan required **by a repeat** assessment no less than 4 weeks from the date of the first documented response.

Complete Response (CR):

The disappearance of all target lesions, non-target lesions, and normalization of tumor markers. Any pathological lymph nodes (whether target or non-target) must have reduction in short axis to <10 mm. There can be no appearance of new lesions.

Confirmation scan required **by a repeat** assessment no less than 4 weeks from the date of the first documented response.

Progressive Disease (PD):

Progressive disease (PD) is defined as radiologic detection of $\geq 20\%$ increase in tumor burden relative to nadir and at least 5 mm absolute increase or unequivocal progression of non-index lesions and confirmation of new lesions.

Stable Disease (SD):

Stable disease (SD) is defined as neither sufficient shrinkage of CR to qualify for PR nor sufficient increase to qualify for PD, taking as reference the smallest sum of diameters since the treatment started.

Unable to evaluate (UE):

Any lesion present at baseline which was not assessed or was unable to be evaluated leading to an inability to determine the status of that particular tumor for that time point.

Measurable baseline disease:

Measurable baseline disease is defined as “Lesions must be accurately measured in at least one dimension (longest diameter in the plane of measurement is to be recorded) with a minimum size of 10 mm by CT scan or MRI. To be measurable a lymph node just

be ≥ 15 mm in short axis when assessed by CT scan or MRI. All tumor measurements must be recorded in millimeters.

Evaluable tumor assessment:

Either of the following assessment must be performed for an evaluable tumor assessment (on or before subsequent anti-cancer therapy):

- **CT/MRI scan to assess tumor response per RECIST 1.1**

The results must be adequate to define a visit response, i.e., a visit overall response other than not evaluable (NE) for RECIST 1.1.

Appendix E. Censoring Rules

Censoring rules for PFS or TTP (radiographic):

Situation up to DCO/EOS	Date of Event or Censoring	Outcome
No evaluable post-baseline or on-study disease assessment; On study without PD or death	Date of the first dose of investigational product (AMG 160)	Censored
PD prior to new anti-cancer therapy	Date of PD	Event
No PD, but death recorded without new anti-cancer therapy	PFS: Date of death; TTP: Date of last evaluable radiographic tumor assessment	PFS: Event; TTP: Censored
Start of new anti-cancer therapy prior to PD or death, or prior to any other disease assessment if there is no PD or death recorded	Date of last evaluable radiographic tumor assessment prior to the start of new anti-cancer therapy	Censored
No PD or death, no new anti-cancer therapy	Date of last evaluable radiographic tumor assessment	Censored
Death or PD immediately after more than one consecutively missed tumor assessment**	Date of last evaluable radiographic tumor assessment prior to the missing assessments*	Censored

DCO: data cutoff; EOS: end of study; PD: progressive disease

* This supersedes the previous rules that result in Event at date of PD or death

**Implementation details: censoring with death or PD immediately after more than one consecutively missed tumor assessment

Scenarios of PD or Death	Censoring Rule	X Days in Censoring Rule
While on treatment	If PD or death is X days after the last scan, censor at the last scan	119

Censoring rules for Duration Of Response (CT/MRI assessment):

Situation up to DCO/EOS	Date of Event or Censoring	Outcome
PD prior to new anti-cancer therapy	Date of PD	Event
No PD, but death recorded without new anti-cancer therapy	Date of death	Event
Start of new anti-cancer therapy prior to PD or death, or prior to any other disease assessment if there is no PD or death recorded	Date of last evaluable tumor assessment by CT/MRI prior to the start of new anti-cancer therapy	Censored
No PD or death, no new anti-cancer therapy	Date of last evaluable tumor assessment by CT/MRI	Censored
Death or PD immediately after more than one consecutively missed tumor assessment**	Date of last evaluable tumor assessment by CT/MRI prior to the missing assessments*	Censored

DCO: data cutoff; EOS: end of study; PD: progressive disease

* This supersedes the previous rules that result in Event at date of PD or death

**Implementation details: censoring with death or PD immediately after more than one consecutively missed tumor assessment

Scenarios of PD or Death	Censoring Rule	X Days in Censoring Rule
While on treatment	If PD or death is X days after the last scan, censor at the last scan	119

Censoring rules for Clinical Progression-free Survival:

Situation up to DCO/EOS	Date of Event or Censoring	Outcome
No evaluable baseline or on-study disease assessment; on study without disease progression or death recorded.	Date of the first dose of investigational product (AMG 160)	Censored
Clinical progression	Date of clinical progression	Event
Death	Date of death	Event
All other scenarios	Date of last assessment	Censored

DCO: data cutoff; EOS: end of study;

Censoring rules for Time to Clinical Progression:

Situation up to DCO/EOS	Date of Event or Censoring	Outcome
No evaluable baseline or on-study disease assessment; on study without disease progression or death recorded.	Date of the first dose of investigational product (AMG 160)	Censored

Clinical progression	Date of clinical progression	Event;
All other scenarios	Date of last assessment	Censored

DCO: data cutoff; EOS: end of study;
